PRF Membrane and Recovery After Periapical Surgery: A 3D Imaging Study

PRF Membrane and Recovery After Periapical Surgery: A 3D Imaging Study

Study Unique Protocol ID:

3736-1/2022/EKU

NCT Number:

Not available

Date of Document:

2024-12-11

Aim

Comparisation of the swelling, the quality of life and the post operative pain after endodontic surgery with and without of the use of A-PRF+.

Materials and methods

Patient selection:

- 10-10 per each group

Inclusion Criteria:

- Adults aged 20-65 years, both male and female.
- Diagnosed with periapical disease, including periapical cysts or granulomas.
- Requiring periapical surgery as part of their treatment plan.
- Presenting a tooth needing endodontic surgery with periradicular lesions of strictly endodontic origin.
- Size of the bone crypt between 6 mm and 12 mm.
- Non-surgical retreatment considered unfeasible or previously failed.
- Apical root canal free from posts over a length of at least 6 mm.
- Adequate coronal restoration without coronal leakage.
- Willing and able to provide written informed consent.
- Capable of attending follow-up visits and participating in required assessments.
- Maxillary and mandibular teeth limited to the 2nd premolar to 2nd premolar regions.
- Without general medical contraindications for oral surgical procedures.

Exclusion Criteria:

- Patients with systemic conditions affecting healing, such as:
 - Uncontrolled diabetes mellitus.
 - Autoimmune disorders.
 - Chronic inflammatory diseases.
- Pregnant or breastfeeding individuals.
- Use of medications or therapies that may interfere with healing, including:
 - Bisphosphonates.
 - Immunosuppressants.
 - Radiotherapy.
 - Oncological therapies (e.g., chemotherapy, immunotherapy).
- Requires antibiotic prophylaxis or therapy.
- History of allergies or adverse reactions to blood-derived products.
- Neuropsychiatric disorders.
- Active infection or severe periodontal disease in the surgical area.
- Periodontal probing depths greater than 5 mm.

- Moderate to severe periodontal bone loss.
- Vertical root fractures.
- Perforation of the furcation area or root canal, except for the apical area.
- Smokers or individuals unwilling to refrain from smoking during the study period.
- Participation in another clinical trial within the last 30 days.
- Absolute or relative contraindications for surgery.

Surgical procedure

- If it is required and feasible endodontic treatment or retreatment maximum 1 week before surgery
- One surgeon perform all operation
- Local anaesthesia 2% lidocaine and ephinephrine 3x2 ml lidocaine
- Trapezoid submarginal flap (Ochsenbein-Luebke flap)
- 15 C surgical blade
- Ball shaped 0,27 mm diameter bone burr, 1:1 straight handpiece
- 3 mm of apical portion is resected- in one piece – perpendicular to the long axis placed in sterile saline
- 3 mm retrograde cavity- with diamond coated ultrasonic instruments
- Microbiological sample
- MTA retrograde RCFilling
- Mobilisation of the flap
- In the test group the resection cavity was filled and covered with A-PRF+ membrane
- Tension free flap closure with 3-0 Silc suture

PRF preparation

- In the test group before surgery 3 or 2 (depends on size of the cavity) 10ml glass tubes without additives
- 1300 rpm for 8 min centrifugation (Harmonycom)
- Using an A-PRF Duo centrifuge (Process for PRF, Nice, France)
- Placed in sterile container (PRF Box, Process for PRF, Nice, France)

Postoperative instruction

- Diclofecan 50mg (Cataflam 50mg) 2x1 per day, for 3 days
- Rinses with 0,12% Chlorehexidine twice a day for 1 week
- No postoperative antibiotics was described
- Suture removal after 7 days

Evaluation

- 3D optical scans (Einstar, Shining 3D) were recorded over two time period, T0 (preoperative scan), T1 (day 3 postoperatively)
- VAS (Visula Analogue Scale) pain was graded on a score to 0-10, 0 no pain, 10 maximum intensity of pain, for 7 days
- Likert scale based questionnaire: ranging from 0 to 4, 0 non 4 very much, for 7 days daily starts on the operation day
 - Postoperative limitations in function: Mouth opening, Chewing, Speaking, Sleeping, Daily routine, Work

Statistical Analisys

Statistical Analysis Plan

1. Study Objectives

- **Primary Objective:**
 - To assess the impact of PRF membrane on postoperative swelling and its relationship with quality of life dimensions and pain.
- **Secondary Objectives:**
 - To compare quality of life (QoL) dimensions and pain levels pre- and post-intervention between the PRF membrane group and the control group.
 - To investigate correlations between swelling (volume) and postoperative QoL dimensions.

2. Study Design

- **Type:** Preliminary comparative study.
- **Groups:**
 - **PRF Membrane Group** (10 participants): Underwent apicoectomy with PRF membrane application.
 - **Control Group** (10 participants): Underwent apicoectomy without PRF membrane.

3. Outcome Measures

1. **Primary Outcomes:**
 - Postoperative swelling (volume): Measured using standardized evaluation methods.
 - Quality of Life (QoL) dimensions: Assessed using a questionnaire with subdimensions (e.g., physical function, pain impact, anxiety, sleep disturbance).
2. **Secondary Outcomes:**
 - Pain intensity: Measured using the Visual Analog Scale (VAS).
 - Correlations between swelling and QoL dimensions.

4. Statistical Methods

1. **Descriptive Statistics:**
 - Mean \pm standard deviation for continuous variables (e.g., QoL scores, pain, swelling volume).
 - Frequency and percentage for categorical variables.
2. **Normality Testing:**
 - **Shapiro-Wilk test:** Conducted for each variable to determine whether parametric or non-parametric tests will be used.
3. **Comparative Analyses:**

- **Between Groups:**
 - Independent samples t-test for normally distributed data.
 - Mann-Whitney U test for non-normally distributed data.
- **Within Groups:**
 - Paired t-test for normally distributed pre- and post-intervention comparisons.
 - Wilcoxon signed-rank test for non-normally distributed data.

4. **Correlations:**

- Spearman's or Pearson's correlation will be used to evaluate the relationship between swelling (volume) and QoL dimensions depending on data distribution.

5. **Significance Threshold:**

- A two-tailed **p-value < 0.05** will be considered statistically significant.

5. Missing Data

- Missing data will be handled by:
 - **Listwise deletion** for analyses where missing data is minimal.
 - Sensitivity analysis if missing data exceeds 10%.

6. Software

- All statistical analyses will be performed using **SPSS** or **R** software.

7. Reporting

- Results will include:
 - Comparative tables of pre- and post-intervention outcomes.
 - Statistical significance levels for group comparisons.
 - Correlation matrices for swelling and QoL dimensions.

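### The primary objective may call for a swelling–pain analysis that is planned nowhere, and the swelling–QoL correlation does not say how treatment group is handled

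*Combined protocol and SAP*

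**What the plan says.** The primary objective (SAP section 1) is "To assess the impact of PRF membrane on postoperative swelling and its relationship with quality of life dimensions and pain". The first secondary objective is comparative: "To compare quality of life (QoL) dimensions and pain levels pre- and post-intervention between the PRF membrane group and the control group". The second concerns correlation: "To investigate correlations between swelling (volume) and postoperative QoL dimensions".

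Three later places take up the correlation, each with QoL as the only partner of swelling:

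- SAP section 3, secondary outcomes: "Correlations between swelling and QoL dimensions".
- SAP section 4, item 4: Spearman or Pearson "will be used to evaluate the relationship between swelling (volume) and QoL dimensions depending on data distribution".
- SAP section 7: "Correlation matrices for swelling and QoL dimensions".

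Pain intensity is a separate secondary outcome, measured by VAS. Under Evaluation in the protocol, VAS is scored 0–10 for 7 days, and a 0–4 questionnaire is completed daily for 7 days from the day of surgery. The scans are at "T0 (preoperative scan), T1 (day 3 postoperatively)", so there is one postoperative swelling measurement per patient. Each group has 10 patients.

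**The concern.** There are two separate gaps.

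**Pain.** If *its* refers to swelling, the primary objective asks how swelling relates to QoL and to pain. Only the QoL half is followed through. Part of the primary objective would then go unanswered although the data are collected.

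**Treatment group.** SAP section 4, item 4 does not say whether the coefficient is computed over all 20 patients, within each group, or adjusted for group. If PRF reduces both swelling and functional limitation, control patients tend to be high on both and PRF patients low on both. A pooled coefficient is then positive even when, on the same treatment, a patient's swelling says nothing about that patient's QoL. It remains a valid description of the overall correlation. Read alone, however, it does not show that more swollen patients fare worse on the same treatment, which is how such a result is easily read.

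**Working it through.** **1. Text check of the pain part.**

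| Place | What is related to swelling |
|---|---|
| SAP 1, primary objective (if *its* = swelling) | QoL dimensions and pain |
| SAP 1, second secondary objective | QoL dimensions |
| SAP 3, secondary outcomes | QoL dimensions |
| SAP 4, item 4 | QoL dimensions |
| SAP 7 | QoL dimensions |

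No section relates swelling to VAS pain. SAP section 3 does offer the impact of pain as an example QoL subdimension. That does not close the gap: the objective lists pain apart from QoL, VAS is the named pain measure, and the six questionnaire items under Evaluation (opening the mouth, eating, speech, sleep, everyday activities, work) include no pain item.

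**2. Correlation produced by group shifts alone.** The plan states no effect size, SD or power, so there is no figure of its own to reproduce. Let PRF shift swelling by d₁ and QoL by d₂ within-group SDs in the same direction, with equal groups and zero within-group correlation. The pooled correlation is

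r = (d₁d₂/4) / √[(1 + d₁²/4)(1 + d₂²/4)], which for d₁ = d₂ = d is (d²/4)/(1 + d²/4).

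- d = 0.5: 0.0625/1.0625 = 0.06
- d = 0.8: 0.16/1.16 = 0.14
- d = 1.0: 0.25/1.25 = 0.20
- d = 1.32: 0.4356/1.4356 = 0.30
- d₁ = 1.32, d₂ = 0.5: 0.165/√(1.4356 × 1.0625) = 0.13

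The value 1.32 SD is what a t-test with 10 per group detects with 80% power. It serves only as an upper reference.

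**3. Critical values.** |r| = t/√(df + t²), two-sided 0.05.

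- Pooled, df 18: 2.101/√(18 + 4.414) = 0.444
- Adjusted for group, df 17: 2.110/√(17 + 4.452) = 0.456
- Within one group of 10, df 8: 0.632

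**4. How often p<0.05 with no within-group link.** Simulation with 40,000 trials per case, 10 + 10 patients. QoL is either normal or a 0–4 item with assumed control-group percentages of 20/20/20/20/20, 10/20/40/20/10 or 40/30/15/10/5. The ranges cover these distributions and both coefficients.

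| Shift in swelling, QoL (SD) | Pooled | Adjusted for group |
|---|---|---|
| 0.5, 0.5 | 5–6% | about 5% |
| 0.8, 0.8 | 8–9% | about 5% |
| 1.0, 1.0 | 11–14% | about 5% |
| 1.32, 1.32 | 19–28% | about 5% |
| 1.32, 0.5 | 8–9% | about 5% |

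For VAS rounded to 0–10, the pooled figures are 6%, 9%, 14% and 27–28% at 0.5, 0.8, 1.0 and 1.32 SD on both variables.

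**5. Price of adjusting.** Assume a within-group r of 0.5 and PRF acting on QoL only through swelling: 1.32 SD on swelling and 0.5 × 1.32 = 0.66 SD on QoL. Power, pooled to adjusted:

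- Normal data: 79% to 62% (Pearson), 72% to 54% (Spearman)
- 0–4 items: 65–74% to 47–56% (Pearson), 63–70% to 45–51% (Spearman)

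**6. Precision.** Fisher 95% interval for an observed r of 0.30, where atanh(0.30) = 0.3095:

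- Pooled: 0.3095 ± 1.96/√17, back-transformed to −0.16 to 0.66
- Adjusted: 0.3095 ± 1.96/√16, back-transformed to −0.18 to 0.66

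**The case against.** The pain gap hangs on one pronoun. The protocol's Aim is purely comparative: "Comparisation of the swelling, the quality of life and the post operative pain after endodontic surgery with and without of the use of A-PRF". The design is described as comparative, and the first secondary objective compares pain between groups. Every mention of correlation stops at QoL, which suggests that no swelling–pain correlation was intended. This stands as a real alternative reading, but it does not settle the matter. Swelling is the nearer noun, and the second secondary objective carries out half of that reading. A primary objective whose required analyses depend on a pronoun needs rewording in any case.

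On pooling, the plan is silent rather than wrong. It asks only for correlations and nowhere claims a within-treatment interpretation. When PRF shifts both variables, the overall correlation is truly non-zero, so the pooled rates above are not false positives for the overall correlation. They are misleading only if the coefficient is taken as the within-group association. All of this stands, and it is why the remedy is to show both coefficients rather than replace one with the other. It is also fair that the larger rates need a strong effect on both variables, that adjusting costs power in a small preliminary study, and that more coefficients means more chances of a nominally significant one.

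**Conclusion.** The concern holds and is minor. On one of two reasonable readings, the pain part of the primary objective has no planned analysis. On either reading, SAP section 4, item 4 leaves open a choice that changes both what the coefficient means and its critical value.

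The practical effect of pooling is small unless PRF strongly affects both variables: at most 9% instead of 5% for shifts up to 0.8 SD on both, and 19–28% only at 1.32 SD on both. These figures rest on assumed effect sizes, zero within-group correlation and assumed score distributions. The finding that the plan is silent on treatment group does not depend on them. The group comparisons of swelling, QoL and pain are not affected.

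**What to change.** 1. **SAP section 1:** replace *its* with the noun intended, swelling or the PRF membrane.
2. **SAP sections 3, 4 (item 4) and 7:** add swelling versus VAS pain. This is required if *its* means swelling, and useful otherwise.
3. **Timing:** swelling is measured once after surgery, while QoL and VAS are recorded over 7 days, so name the day to be correlated. Pair the day-3 swelling with the QoL and VAS scores of the same postoperative day. State how days are counted, because the questionnaire starts on the day of surgery.
4. **Treatment group:** report a partial correlation (Pearson or Spearman) adjusted for group next to the pooled one, both with 95% CIs, and name the interval method. Say that the pooled coefficient describes the overall association and the adjusted one the association between patients on the same treatment. A pooled coefficient alone should not be read as evidence of the latter.

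If all six items are used, this gives 7 pairs (six items plus VAS) and 7 × 2 = 14 coefficients. They should be labelled exploratory and read mainly through their intervals.

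The cost is SAP wording and a few lines of code on data already collected. The adjusted coefficient gives up one degree of freedom and, where PRF acts on QoL through swelling, some power, as shown above. Keeping the pooled coefficient beside it means that this loss does not remove any information the current plan would provide.

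### The primary QoL outcome has no fixed score or day, its examples do not match the described questionnaire, and its rank and pre/post comparison conflict with other text

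*Combined protocol and SAP*

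**What the plan says.** SAP section 3 lists two primary outcomes, swelling volume and QoL dimensions. The second is "Assessed using a questionnaire with subdimensions (e.g., physical function, pain impact, anxiety, sleep disturbance". No instrument is named.

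The Evaluation section describes one questionnaire. It is scored 0 to 4, its content is "Postoperative limitations in function: Mouth opening, Chewing, Speaking, Sleeping, Daily routine, Work", and it is completed "for 7 days daily starts on the operation day". Pain intensity is recorded separately on a 0-10 VAS for 7 days, with no start day given. Swelling is scanned twice, at a preoperative T0 and at "T1 (day 3 postoperatively".

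The primary objective in SAP section 1 is "To assess the impact of PRF membrane on postoperative swelling and its relationship with quality of life dimensions and pain". The secondary objectives are "To compare quality of life (QoL) dimensions and pain levels pre- and post-intervention between the PRF membrane group and the control group" and "To investigate correlations between swelling (volume) and postoperative QoL dimensions". In section 3, pain intensity and "Correlations between swelling and QoL dimensions" are secondary outcomes.

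Section 4 plans between-group tests (t-test or Mann-Whitney), paired within-group tests and correlations, all at two-sided p < 0.05. Section 7 promises pre/post tables and correlation matrices.

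**The concern.** A primary outcome should let a second analyst compute the same number from the same data. Here the analyst has an example list that only partly matches the collected items, no rule for combining six items, and no rule for choosing or summarising seven days. The result that is called the QoL finding can then be settled after the data are seen.

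The conflicting ranks add to this, because a reader cannot tell whether the QoL group comparison or the swelling-QoL relationship answers the primary question. The pre/post wording also promises a QoL and pain analysis for which the documents show no starting value.

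**Working it through.** **1. Examples against items.**

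| Example in SAP section 3 | Item in Evaluation |
|---|---|
| Physical function | Several related items, no stated scoring |
| Pain impact | None (the VAS measures intensity and is a separate outcome) |
| Anxiety | None |
| Sleep disturbance | Sleeping |

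One of four matches, one matches loosely and two have no item.

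**2. Open comparisons.** 6 items x 7 days = 42 between-group tests, or 6 x 6 = 36 without the operation-day entry. Neither figure is a ceiling: daily sums, peaks and item means are also open.

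**3. Size.** The plan gives no figure to reproduce. If the tests were independent, the chance of at least one p < 0.05 with no true effect would be 1 - 0.95^42 = 0.884, and 1 - 0.95^6 = 0.265 for six items on one day. Item-days within a patient are correlated, so this was simulated with 10 per group, Mann-Whitney at two-sided 0.05, and 12,000 trials per setting. Two inputs are assumptions, not in the documents: answers 0 to 4 with probabilities 35/30/20/10/5%, and the latent correlation r.

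| At least one p < 0.05 | r = 0.3 | 0.5 | 0.7 | 0.9 |
|---|---|---|---|---|
| 42 tests, equal correlation | 0.751 | 0.612 | 0.441 | 0.243 |
| 42 tests, correlation x 0.8 per day apart | 0.702 | 0.653 | 0.561 | 0.439 |
| 36 tests, equal correlation | 0.704 | 0.572 | 0.413 | 0.232 |
| 6 items, one day | 0.222 | 0.203 | 0.162 | 0.121 |
| One score (mean of daily sums) | 0.046 | 0.043 | 0.042 | 0.046 |

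The Monte Carlo standard error is at most 0.005. The simulation uses Mann-Whitney throughout, whereas the SAP chooses between the t-test and Mann-Whitney after Shapiro-Wilk. For the single score, the t-test gave 0.047 to 0.051.

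**4. Ranks.**

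| Quantity | Section 1 | Section 3 |
|---|---|---|
| QoL group comparison | Secondary objective | QoL is a primary outcome |
| Swelling-QoL relationship | Primary and secondary objective | Secondary outcome |
| Pain | Primary objective (relationship with swelling) and secondary objective (group comparison) | Secondary outcome |

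**5. Baseline.** Swelling has T0. The questionnaire concerns postoperative limitations and begins on the operation day; whether that entry precedes surgery is not stated. The VAS start is not stated either. No preoperative value is therefore documented for QoL or pain.

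**6. Pairing with T1.** Swelling has one postoperative scan and the questionnaire has seven days. If the operation day is day 0, day 3 is the fourth entry; if it is day 1, the third. The SAP fixes neither the day nor the score for the correlation.

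**The case against.** The strongest defence is that the subdimensions are only examples, that the six items and the schedule are in the document, and that this is a preliminary study whose tables and correlation matrices will show results broadly. Part of this stands. The example mismatch alone would be a wording correction, the preliminary label tempers the error-rate argument, and broad tables limit selective reporting. None of it says which result counts as the primary QoL result, or links the SAP outcome to the six items.

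Listing QoL as a primary outcome is not in itself contradictory, because the primary objective names QoL. The conflict is the secondary label on its group comparison and the mixed rank of the swelling-QoL relationship.

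Four stronger readings are tempting, and the documents do not support them:

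- A reader might infer that the pre/post QoL comparison is impossible. The operation-day entry could precede surgery; the text leaves this open. What can be said is that no preoperative value is documented.
- A reader might infer that the paired tests and pre/post tables in sections 4 and 7 are unusable. They are worded generically, and the T0 and T1 scans satisfy them for swelling.
- A reader might infer that listwise deletion would remove most patients. With 2% of answers blank, 1 - 0.98^42 = 57% would be lost, but only for a score needing all 42 answers. The SAP defines no such score, and section 5 reserves listwise deletion for minimal missingness.
- A reader might take the equal-correlation figures as a worst case. The decaying pattern gives higher values at r = 0.5 to 0.9.

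**Conclusion.** The point holds. The QoL primary outcome is tied to no score or day, two of its four examples have no item in the only questionnaire described, its ranks conflict between sections 1 and 3, and section 1 promises a pre/post comparison of QoL and pain without a documented starting value.

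If the result were chosen from the 42 item-days, the chance of at least one false positive would be about 75% to 24% under equal correlation of 0.3 to 0.9, or about 70% to 44% if correlation decays over days. One score fixed before data are seen gives about 5%. These figures illustrate the freedom left open and rest on the assumed response probabilities and correlations; the documents do not say that all 42 tests will be run. The textual conflicts do not depend on them. The plan should be corrected.

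**What to change.** All changes are to SAP text and need no new data collection.

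1. In section 3, replace the examples with the six collected items and call the outcome postoperative limitation in function. If another instrument was used, describe its items, scoring and days under Evaluation.
2. Make sections 1 and 3 agree on rank for QoL, pain and the swelling correlations.
3. Prespecify one summary score for the group comparison, for example the mean over days of the six-item sum (0 to 6 x 4 = 24). Say whether the operation-day entry is before or after surgery and whether it counts. Report single items as supportive.
4. Compute the score from available entries under a stated minimum, so that one blank item does not remove a patient.
5. In section 1, remove the pre/post comparison of QoL and pain unless preoperative values exist; if they do, describe them. Otherwise state that the paired tests and pre/post tables in sections 4 and 7 apply to swelling only.
6. Prespecify the questionnaire day and the score to be correlated with swelling at T1, and state how days are counted.
7. Date the change. The past tense used for the scans and the groups suggests that data may exist; if any have been seen, disclose it, because error control then no longer holds in full.

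Costs: the claim narrows from quality of life to limitation in function. An equal-weight sum can also miss an effect on one item. In simulation (r = 0.5, 1 SD latent shift), its power is about 81% if all six items shift, but only about 6-7% if one does, against about 73% for that item tested alone. The score and the minimum are choices among several; fixing them in advance is what matters. Swelling and QoL would remain two unadjusted primary tests, with a joint error of up to 1 - 0.95^2 = 0.0975 if independent, unless one is ranked first.

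### VAS pain is recorded for 7 days, but the SAP does not say how those scores enter the group comparison and specifies no analysis of the repeated scores

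*Combined protocol and SAP*

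**What the plan says.** The protocol's Evaluation section states that VAS "pain was graded on a score to 0-10, 0 no pain, 10 maximum intensity of pain, for 7 days". The word for daily recording is attached only to the Likert questionnaire, but seven daily pain scores is the natural reading.

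SAP section 1 sets as a secondary objective "To compare quality of life (QoL) dimensions and pain levels pre- and post-intervention between the PRF membrane group and the control group". SAP section 3 lists the secondary outcome as "Pain intensity: Measured using the Visual Analog Scale (VAS)" and names no day, peak, mean or area under the curve.

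SAP section 4.3 offers two between-group methods, "Independent samples t-test for normally distributed data" and "Mann-Whitney U test for non-normally distributed data". The within-group methods are "Paired t-test for normally distributed pre- and post-intervention comparisons" and its signed-rank counterpart. Section 4.5 sets a two-sided 0.05 threshold and mentions no adjustment. Section 5 uses listwise deletion when little is missing, with a sensitivity analysis above 10%. Section 7 promises pre/post tables, significance levels for the group comparisons and correlation matrices. The size is "10-10 per each group", with no power calculation.

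**The concern.** The data have seven time points, and the analysis plan is written for one or two. An analyst following the SAP must decide which pain value goes into the test, and the SAP gives no basis for the choice. Each route has a cost:

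- **One day.** The day can be chosen after the data are seen, and the other six scores are not used.
- **Every day.** This gives seven tests at 0.05 with no rule for reading them together.
- **A weekly summary.** This would be sound, but none is defined, and neither is the handling of a diary with gaps.

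Pain is in the trial's Aim, in the primary objective (through its relationship with swelling) and in a secondary objective. With 10 patients per arm there is little precision to spare.

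**Working it through.** The plan states no effect size, SD or power, so there is no figure of its own to reproduce.

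**Inputs from the documents:** 10 patients per arm (protocol, Patient selection; SAP section 2); 7 days of VAS (protocol, Evaluation); two-sided 0.05 (SAP section 4.5); listwise deletion (SAP section 5).

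**Assumptions:** one score per day, the same SD on every day (the unit below), and an equal correlation ρ between any two days. The documents give no ρ, so a range is shown.

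**Step 1. Precision of one day against the 7-day mean.** The variance of a mean of seven equally correlated scores, relative to one score, is (1 + 6ρ)/7.

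| ρ | (1 + 6ρ)/7 | SD ratio, mean to one day | SE of one day relative to the mean |
|---|---|---|---|
| 0.4 | 3.4/7 = 0.486 | 0.697 | 1/0.697 = 1.43 |
| 0.6 | 4.6/7 = 0.657 | 0.811 | 1/0.811 = 1.23 |
| 0.8 | 5.8/7 = 0.829 | 0.910 | 1/0.910 = 1.10 |

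For one day with 10 per arm, the 95% CI half-width is t(0.975; 18 df) × √(2/10) = 2.101 × 0.447 = 0.94 SD. For the 7-day mean it is 0.94 times the SD ratio: 0.65, 0.76 and 0.86 SD.

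**Step 2. Power if the effect is the same on all seven days.** With a two-sample t-test (noncentral t), one day has 80% power for a difference of 1.325 SD and 56% power for 1 SD. For the 7-day mean, the detectable difference is 1.325 times the SD ratio: 0.92, 1.07 and 1.21 SD. Power for 1 SD is 86%, 74% and 64%.

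**Step 3. Power if the effect is confined to 3 of the 7 days.** A 1-SD effect on three days averages 3/7 = 0.429 SD over the week. Divided by the SD ratio this is 0.61, 0.53 and 0.47 standardised units, with power 26%, 20% and 17%. A test on one affected day keeps 56%. The gain in Step 1 therefore concerns the week-average effect and is not a general gain in power.

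**Step 4. Testing each day at 0.05.** If days were independent, the chance of at least one false positive is 1 − 0.95⁷ = 0.30. In 100,000 simulated trials with 10 per arm it was 27%, 24%, 19% and 12% at ρ = 0.3, 0.5, 0.7 and 0.9.

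**Step 5. Missing days.** If 5% of scores were missing on each day, independently (an assumption), 0.95⁷ = 0.70 of diaries would be complete, or about 14 of 20 patients. Listwise deletion in a whole-diary analysis would drop the other six.

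**The case against.** A reader might infer that, because the listed tests take one value per patient, the plan cannot use the whole diary and so necessarily loses precision. The documents do not support that. A t-test or Mann-Whitney test on each patient's 7-day mean takes one value per patient and uses every score. With complete data it loses no precision against a mixed model for the average effect. The SAP names no single day and does not exclude a summary. The loss in Step 1 is therefore conditional on single-day testing.

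Three further objections have weight. First, nothing in the documents supports an equal effect on all seven days, and the protocol's postoperative analgesic is prescribed for 3 days only, so conditions differ within the diary. Step 3 shows that a 7-day mean can then have less than half the power of one well-placed day. Second, the stated objective speaks of pre- and post-intervention pain levels, not of the course of pain over a week. Third, this is a secondary outcome in a preliminary study, and a normal-theory model for a bounded 0–10 score in 20 patients needs a non-parametric check.

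These points limit the size of the claim and shape the remedy. They do not close the gap: the objective does not say which of the seven scores counts as post-intervention, and silence about the tested value is itself the defect.

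**Conclusion.** The point holds as a gap in specification with conditional consequences. The SAP does not define how the 7-day pain scores enter the group comparison, and it specifies no analysis that uses them as repeated scores.

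If single days are tested, the standard error for the week-average effect is about 1.1 to 1.4 times that of the 7-day mean at ρ = 0.8 to 0.4. If every day is tested, the chance of at least one false positive is about 12% to 30%. The first range assumes equal daily SDs and equal correlation. The second depends on ρ, and its upper end is the independent case. Both assume daily scoring.

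An unconditional statement that the PRF effect on pain will be estimated less precisely than the data allow would go beyond the documents. So would a claim that a 7-day mean always raises power. The change is still worth making, because each reading of the present text leaves a choice open and the remedy needs no new data. The same gap affects the quality-of-life questionnaire, which is explicitly daily for 7 days and which SAP section 3 lists as a primary outcome.

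**What to change.** In SAP section 4.3, name one pain comparison: the between-group difference in the mean of the seven daily VAS scores, with its 95% CI. Estimate it from a mixed model with group, day (categorical) and group-by-day as fixed effects and patient as random effect, so that incomplete diaries still contribute. In SAP section 5, state that listwise deletion does not apply to this analysis.

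Report the seven daily differences with CIs as description only. Apply the Mann-Whitney test to each patient's 7-day mean as a non-parametric check. Call the quantity a mean, not an area under the curve divided by 7: seven points span six intervals, so under the trapezoidal rule a constant score of 1 would give 6/7 = 0.857.

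State in the protocol that VAS pain is scored daily, and define in the same way how the daily questionnaire scores enter their comparison.

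The cost is SAP wording and one model, which either software package in SAP section 6 can fit. The downside is the dilution in Step 3. If the sponsor expects an early effect, a shorter early window should be prespecified in place of the 7-day mean, before any outcome data are examined.
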